8.8.1. Laboratory Values Meeting Hy's Law Criteria

All occurrences of possible drug-induced liver injury that meet Hy's law criteria as defined in the Section 7.1.5.1 of the study protocol will be included in serious adverse events reporting.

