7.1.5.1. Definition of a Serious Adverse Event

A serious adverse event is an adverse event occurring at any dose that results in any of the following outcomes or actions:

- results in death
- is life-threatening adverse event (ie, the patient was at risk of death at the time of the event); it does not refer to an event which hypothetically might have caused death if it were more severe
- requires inpatient hospitalization or prolongation of existing hospitalization, which means that hospital inpatient admission or prolongation of hospital stay were required for treatment of an adverse event, or that they occurred as a consequence of the event
Hospitalizations scheduled before the patient signed the ICF will not be considered serious adverse events, unless there was worsening of the preexisting condition during the patient's participation in this study.
- results in persistent or significant disability/incapacity (refers to a substantial disruption of one's ability to conduct normal life functions)
- is a congenital anomaly/birth defect
- an important medical event that may not result in death, be life-threatening, or require hospitalization, but may jeopardize the patient and may require medical intervention to prevent one of the outcomes listed in this definition

Examples of such events are intensive treatment in an emergency room or at home for allergic bronchospasm; blood dyscrasias or convulsions that do not result in hospitalization; or the development of drug dependency or drug abuse. Note: Any suspected transmission of an infectious agent via a medicinal product is considered an important medical event.

All occurrences of possible drug-induced liver injury that meet Hy's law criteria, defined as **all** of the below, must be reported by the investigator to the sponsor as a serious adverse event:

- ALT or AST increase of $\geq 3 \times$ the ULN
- total bilirubin increase of $\geq 2 \times$ ULN
- absence of initial findings of cholestasis (ie, no substantial increase of ALP)
- no other explanation for the observed abnormalities

An adverse event that does not meet any of the criteria for seriousness listed above will be regarded as a nonserious adverse event.

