8.8. Clinical Laboratory Tests

Clinical laboratory tests (serum chemistry, hematology, coagulation, and urinalysis; see protocol Appendix M) will be performed at visits 4, 7, 10 and 11 using the central laboratory. All clinical laboratory test results outside of the reference range will be judged by the investigator as belonging to one of the following categories:

- abnormal and not clinically significant
- abnormal and clinically significant

A laboratory test result that is judged by the investigator as clinically significant will be recorded on the source documentation and the CRF as an adverse event, and monitored as described in Section 7.1.2 of the protocol.

Laboratory test results will be presented in standard international (SI) units in summaries. Laboratory values and changes from baseline to each visit and Last Assessment will be summarized using descriptive statistics. Shifts (below [low], within [normal], and above [high] the normal range) from baseline to each postbaseline visit and the Last Assessment will be summarized using patient counts. Baseline is defined as the last observed data before the administration of the first dose of the IMP in the pivotal study.

The potentially clinically significant abnormal values will be derived using criteria specified in Table 4 based on all postbaseline values (including scheduled, unscheduled, and withdrawal visits). The overall incidence of potentially clinically significant abnormal values will be summarized for laboratory variables using descriptive statistics by treatment group. Listings for patients who have potentially clinically significant abnormal laboratory data will be presented.

Table 4: Criteria for Potentially Clinically Significant Laboratory Values

Test		Criterion value
Serum chemistry		
ALT		≥3x ULN
AST		≥3x ULN
ALP		≥3x ULN
GGT		≥3x ULN
LDH		≥3x ULN
BUN		≥10.71 mmol/L
Creatinine		≥177 µmol/L
Bilirubin (total)		≥34.2 µmol/L
Hematology		
Hematocrit	Men	<0.37 L/L
	Women	<0.32 L/L
Hemoglobin	Men	≤115 g/L
	Women	≤95 g/L
WBC counts		≤3 x 10 ⁹ /L
		≥20 x 10 ⁹ /L
Eosinophils		≥10%
ANC		$\leq 1 \times 10^9/L$
Platelet counts		≤75 x 10 ⁹ /L
		≥700 x 10 ⁹ /L
Urinalysis		
HGB		≥2 unit increase from baseline
Glucose		≥2 unit increase from baseline
Ketones		≥2 unit increase from baseline
Total protein		≥2 unit increase from baseline

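### Every planned Hy's law count rests on investigator-reported events; no output counts, from laboratory data, patients with ALT or AST ≥3 × ULN together with total bilirubin ≥2 × ULN

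*SAP*

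**What the plan says.** Protocol 7.1.5.1 defines a Hy's law case by four conditions that must all hold: ALT or AST at least 3 × ULN, total bilirubin at least 2 × ULN, no initial cholestasis (judged by ALP, with no numeric limit), and "no other explanation for the observed abnormalities". Such a case "must be reported by the investigator to the sponsor as a serious adverse event".

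SAP 8.8.1 relies on that route. Cases "as defined in the Section 7.1.5.1 of the study protocol will be included in serious adverse events reporting", and nothing further is specified under that heading.

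There is a second route. Protocol 7.1.7 and SAP 8.3 make Hy's law events AESIs. They do the same for possible liver injury, where ALT or AST, bilirubin, or INR each qualifies alone. SAP 8.3 plans a summary of AESIs, overall and by severity, and a listing.

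Laboratory data are handled in SAP 8.8: "The potentially clinically significant abnormal values will be derived using criteria specified in Table 4 based on all postbaseline values". Table 4 has one row per test. ALT and AST are flagged at 3 × ULN or more and total bilirubin at 34.2 µmol/L or more. Then: "The overall incidence of potentially clinically significant abnormal values will be summarized for laboratory variables using descriptive statistics by treatment group". Patients with flagged values are also listed.

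**The concern.** The heading of SAP 8.8.1 leads the reader to expect a result computed from laboratory values, and none is planned. Both outputs that could show a Hy's law case, the SAE tables and the AESI tables, contain what a site chose to file. The laboratory tables use measured values but never join the enzyme and bilirubin conditions in one patient.

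Long-term safety is the primary objective (SAP 1.1), liver enzyme elevation is a named potential risk (protocol 1.3.1), and there is no Data Monitoring Committee (protocol 5.9.3). The values needed are already collected. Such events are rare, so a report of none or one matters, and it should not depend on site reporting when it can be checked against the data.

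**Working it through.** The documents state no figure on this point, so there is nothing to reproduce. The check sets the planned outputs against the definition and then asks whether the separate counts could yield the joint one.

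**Step 1. Outputs that bear on Hy's law**

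| Output | Source | Joins enzymes and bilirubin? |
|---|---|---|
| SAE summary and listing (SAP 8.3, 8.8.1) | Investigator report | Only through the investigator's judgment |
| AESI summary and listing (SAP 8.3) | Investigator report | Hy's law events are named; the other liver criteria are alternatives |
| Incidence of flagged values (SAP 8.8, Table 4) | Laboratory data | No, one variable at a time |
| Listing of flagged patients (SAP 8.8) | Laboratory data | By hand search; no count |
| Shift tables (SAP 8.8) | Laboratory data | No |

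In SAP 8.3 patients are counted by preferred term or system organ class, and no separate Hy's law row is stated. Events with a missing seriousness flag are left out of the SAE summary.

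**Step 2. What the laboratory flags guarantee**

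The Table 4 limit for ALT and AST, 3 × ULN, is the same as the enzyme condition in protocol 7.1.5.1. Every patient who meets that condition in the postbaseline laboratory data is therefore flagged, counted and listed. The number of patients with an ALT or AST flag is an upper bound on the joint count. If it is zero, the joint count is zero.

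**Step 3. What they do not give**

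Let *a* be the number of patients flagged for ALT or AST, *b* the number flagged for bilirubin, and *N* the number treated. The number with both flags lies between max(0, *a* + *b* − *N*) and min(*a*, *b*). Take *N* = 360, the planned number treated (SAP 2.1). The values of *a* and *b* are assumed.

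- *a* = 3, *b* = 2: max(0, 3 + 2 − 360) = 0, min = 2, so 0 to 2 patients.
- *a* = 5, *b* = 4: 0 to 4 patients.
- *a* = 10, *b* = 6: 0 to 6 patients.

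The two incidence figures leave the joint count undetermined in each case. The bound uses Table 4's own bilirubin limit, which equals 2 × ULN only when the ULN is 34.2 / 2 = 17.1 µmol/L. The documents give no ULN. For the protocol's bilirubin threshold, *a* alone is the safe upper bound unless the ULN is at least 17.1 µmol/L.

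**Step 4. Timing**

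The flags are taken over any postbaseline visit. Scheduled samples fall at visits 4, 7, 10 and 11 (weeks 12, 24, 36 and 40). A patient with both flags may have had them 12 weeks or more apart, so a joint count needs a stated time window.

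**Step 5. What laboratory values can and cannot establish**

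The enzyme and bilirubin conditions can be derived directly. The ALP condition needs a limit that the protocol does not give. The absence of another explanation is a clinical judgment. A derived count is therefore a screen for possible cases.

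**The case against.** The strongest reply is that a case would be hard to lose. It is reportable as an SAE and as an AESI, and the enzyme and bilirubin criteria each trigger AESI reporting alone. Protocol Appendix J requires confirmation and follow-up of ALT or AST at 3 × ULN or more, with results recorded in the CRF. Appendix S says data from external sources, including the central laboratory, are compared with the clinical database and discrepancies queried. Protocol 7.1.2 and 7.4 also point to monitoring plans that are not available here. Routing judged cases through SAE reporting is consistent with a definition that includes clinical judgment, and the analysis is descriptive (SAP 7).

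Most of this stands, and it rules out three stronger readings that a reader might infer:

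- **SAE reports are the only source.** They are not; SAP 8.3 plans AESI outputs that name Hy's law events.
- **Nothing in the plan would reveal an unreported case.** The patient would appear in the ALT or AST incidence and in the listing, by Step 2.
- **The fixed bilirubin limit hides cases.** For an assumed ULN of 15 to 22 µmol/L, 2 × ULN is 30 to 44 µmol/L, so the limit can lie on either side. It cannot remove a qualifying patient from the listing, because the enzyme flag alone puts the patient there.

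The reply does not supply the joint count. The Appendix S check is generic and does not mention comparing laboratory patterns with SAE or AESI reports. The listing gives no total, and the SAP does not say whether it shows all liver values of a flagged patient or only the flagged ones.

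**Conclusion.** The point holds as a modest improvement. Reported events are the basis of every planned Hy's law count, and no planned laboratory output counts patients who meet the enzyme and bilirubin conditions together. The size cannot be stated beyond the bound in Step 3: the joint count lies between zero and the number of patients with an ALT or AST flag, and it is settled in advance only if that number is zero.

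This rests on the visible text of the SAP and on the assumption that no unseen monitoring or laboratory plan specifies such an output. It does not show that any case would be missed, and it does not make the SAE route wrong. The gain is that the reported number can be checked against measured values.

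**What to change.** In SAP 8.8.1, add a count and a patient listing, by treatment group and indication, of patients with ALT or AST ≥3 × ULN and total bilirubin ≥2 × ULN in the same sample or within a stated window.

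- Use all postbaseline laboratory values, scheduled and unscheduled, and say whether local results recorded under Appendix J are included.
- Use ULN multiples for both conditions, as in protocol 7.1.5.1.
- Show ALP alongside, and give the investigator's judgment on other explanations its own column.
- Label the output a biochemical screen, not confirmed Hy's law.
- Reconcile it with the SAE and AESI reports before database lock.

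The cost is one derived flag, one count and one listing from data already held. Table 5 already applies a two-part criterion to vital signs, so the programming is familiar. The downside is that a few biochemical cases with another cause will be listed and need explanation.

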8.9. Physical Examinations

Physical examinations will be performed at visits 2, 4, 5, 7, 8, 10, 11, and 12. Any physical examination finding that is judged by the investigator as a clinically significant change (worsening) compared with a baseline value will be considered an adverse event, recorded on the CRF, and monitored as described in Section 7.1.2 of the study protocol.

Abnormal physical examination findings will be listed.

Weight will be summarized and listed with vital signs data.

8.10. Vital Signs

Vital signs (pulse, systolic and diastolic blood pressure, and body temperature) will be measured at each (visit 2 through 12). Weight will be measured at visits 2, 4, 5, 7, 8, 10, 11, and 12. Any vital sign value that is judged by the investigator as a clinically significant change (worsening) from a baseline value will be considered an adverse event, recorded on the source documentation and transcribed onto the CRF, and monitored as described in Section 7.1.2 of the protocol.

Vital signs (including weight) values and changes from baseline to each visit and the Last Assessment will be summarized using descriptive statistics. The incidence of potentially clinically significant abnormal values will be summarized for selected vital signs using descriptive statistics. Baseline is defined as the last observed data before the administration of the first dose of the IMP in the pivotal study.

Table 5 specifies the criteria for identifying vital signs as potentially clinically significant abnormal values. Note that in order to qualify as potentially clinically significant abnormal, a value needs to meet both criteria below: ie, have a value beyond the criterion value and a change of at least the magnitude specified in the change relative to baseline column. The potentially clinically significant abnormal vital signs values will include all postbaseline values (including scheduled, unscheduled, and early withdrawal visits) for the summaries.

Table 5: Criteria for Potentially Clinically Significant Vital Signs

Vital Sign	Criterion value	Change relative to baseline
Pulse	≥120 bpm	Increase of ≥15 bpm
	≤50 bpm	Decrease of ≥15 bpm
Systolic blood pressure	≥180 mm Hg	Increase of ≥20 mm Hg
	≤90 mm Hg	Decrease of ≥20 mm Hg
Diastolic blood pressure	≥105 mm Hg	Increase of ≥15 mm Hg
	≤50 mm Hg	Decrease of ≥15 mm Hg
Temperature	≥38.3°C	Change of ≥1.1°C

bpm=beats per minute

8.11. Electrocardiography

Triplicate 12-lead ECGs will be collected at visits 4, 7, 10 and 11. Any ECG finding that is judged by the investigator as a potentially clinically significant change (worsening) compared with a baseline value will be considered an adverse event, recorded on the source documentation and in the CRF, and monitored as described in Section 7.1.2 of the protocol.

For ECG variables, the mean of recorded results from the 3 measurements at a visit will be calculated. The mean results and mean changes from baseline to each visit and Last Assessment will be summarized using descriptive statistics. Baseline is determined based on the last set of observed data before the administration of the first dose of the IMP in the pivotal study.

For ECG findings, the worst value of recorded findings at a visit will be used for analysis. Baseline ECG findings and shifts (normal, abnormal not clinically significant, and abnormal clinically significant) from baseline to overall (worst value for a patient) and the Last Assessment (worst value of recorded findings from the last visit) will be summarized using patient counts.

8.12. Concomitant Medications or Therapies

Concomitant medications, treatments, or procedures will be collected up to the end of study.

All concomitant medications will be coded using the WHO Drug. The incidence of concomitant medications will be summarized using descriptive statistics by therapeutic class and preferred term. Patients are counted only once in each therapeutic class category, and only once in each preferred term category. The concomitant medications will include all medications taken after administration of the first IMP.

The subset of medications or therapies will be summarized by the indication categories as indicated in Section 5.5.

Concomitant medications for patients who are enrolled in this study for the evaluation of ADA only will be listed.

9. TOLERABILITY VARIABLES AND ANALYSIS

Tolerability was not specifically defined for this study.

10. PHARMACOKINETIC ANALYSIS

There are no prespecified pharmacokinetic endpoints.

Summary of plasma concentration of the study drug will be based on the safety population and will be presented by visit for each of the indication (CCH or ECH) and active treatment groups (and the treatment received in 056 and 057 studies). The plasma concentration will be listed by indication, active treatments, scheduled visits, and time points.

11. PHARMACOGENOMIC ANALYSIS

Pharmacogenomic analysis results will be summarized for each gene tested. An attempt will be made to correlate clinical observations (pharmacokinetics, safety, efficacy, or other effects) with the genotypes observed. Additional pharmacogenomic analysis may be conducted at a later time and will be reported in a separate addendum report.

This analysis is not included in this SAP.

12. BIOMARKER ANALYSIS

Biomarker analysis will include logistic regression, receiver operating characteristic curves, and summary statistics. This analysis will be reported separately. Measurements will be made using validated assays.

This analysis is not included in this SAP.

13. IMMUNOGENICITY ANALYSIS

A summary of immunogenicity results will be provided, and the incidence of immunogenicity will be calculated. The impact of immunogenicity on the pharmacokinetic profile, IMP efficacy, and clinical safety will be evaluated. This ADA impact analysis will be reported separately.

This analysis is not included in this SAP.

15. PLANNED INTERIM ANALYSIS

Not applicable.

16. STATISTICAL SOFTWARE

All data listings, summaries, and statistical analyses will be generated using SAS®.

17. CHANGES TO ANALYSES SPECIFIED IN THE STUDY PROTOCOL

[figure not shown]
None.

[figure not shown]

APPENDIX A.

APPENDIX C.	
	_ _
Self-Care	0
	_ _
	_
	_
	_ _
	-
	 

APPENDIX D.

D	A	Question/Response	D	A	Question/Response
Ī					
			Ī		
2					

Statistical Analysis Plan

D	A	Question/Response	D	A	Question/Response
1					

Scoring:			

APPENDIX E.

ALLENDIA				
Scale	Label	Item#	Question	Response
				5=None of the time

i E

APPENDIX F.

Question (baseline visit)	Response

Question (baseline visit)	Response

APPENDIX G.

Question (at baseline visit)	Response

Statistical Analysis Plan

Question (at baseline visit)	Response
